# **3 TRIAL SYNOPSIS**

Clinical Trial Title: A Randomized, Evaluator Blinded, Within Subject, Single-Centre evaluation of the Vasoconstriction Properties of MC2-01 cream, compared to 5 Other Corticosteroids in Healthy Subjects.

#### Short Title :

A vasoconstriction test trial with a MC2-01 cream (ranking trial).

Sponsor Trial Number:	MC2-01-C4
Clinical Trial Phase:	Phase 1
Investigator:	[name] [name]
Co-Investigator:	[name] [name]
Clinical Trial Population:	Healthy subjects, males and females, aged 18 to 50 years old.
Clinical Trial Objectives:	The objective of this trial is to compare the vasoconstriction potential (skin blanching effect) of MC2-01 cream with Clobex 0.05% (clobetasol propionate) lotion, Betamethasone Dipropionate (Augmented) 0.05% (betamethasone dipropionate) cream, Triamcinolone Acetonide 0.1% (triamcinolone acetonide) cream, Locoid ® 0.1% (hydrocortisone butyrate) cream, Desowen ® 0.05% (desonide) cream and MC2-01 vehicle using the human skin blanching test (McKenzie-Stoughton's test).
Background:	Topically applied corticosteroids elicit a pharmacologic activity (blanching) viewed by many as being "vasoconstrictive" in nature. The skin blanching effect was first described by Mc Kenzie and Stoughton (1) in 1962. This pharmacodynamic response has been correlated with the clinical efficacy of the product in psoriasis (2) and used for years to determine the clinical potency of topical corticosteroid formulations and to classify them within the US topical steroid potency classification.
	MC2 Therapeutics has developed an innovative dermal pharmaceutical formulation containing calcipotriol (CAL) 0.005 % w/w (50 $\mu$ g/g) and betamethasone dipropionate (BDP) 0.064 % w/w (0.5 mg/g as betamethasone), MC2-01 cream to ease local application of pharmaceuticals and to significantly enhance local cutaneous penetration of the active ingredients.
	Currently marketed products are restricted to non-oil-based formulations as calcipotriol and betamethasone are characterized by having a potential incompatibility to exist together in an environment, since calcipotriol requires basic conditions to maintain stability while betamethasone requires acidic conditions.

CPCAD Nice	C P C A D
Clinical Trial Protocol MC2-01-C4	Final Approved Version 20/08/2018
	MC2-01 cream has been formulated using the PAD ™ Technology allowing sufficient protection of the drug substances from degradation during storage.
Clinical Hypothesis:	The blanching effect of the MC2-01 cream is expected to be lower than Clobex, not significantly different from Betamethasone Dipropionate (Augmented) cream and higher than the other references.
Clinical Trial Design:	A single center, single application, randomized, investigator blinded, active and vehicle controlled, intra-individual comparison in healthy volunteers.
	The subjects will be screened within 2 weeks prior to the Day 1 and then receive a single application of investigational and reference products. All applications will be done on site by a qualified person. The Investigational products will be tested under non-occlusive condition for 16 hours.
	Clobex lotion (Galderma Labs LP), Betamethasone Dipropionate (Augmented) cream (Taro Pharmaceuticals), Locoid® cream (Precision dermatology), Desowen® cream (Galderma Labs LP) and Triamcinolone Acetonide (Ascend Laboratories LLC) will be used as positive controls. The MC2-01 matching vehicle will be used as negative control.
	Hence, the seven treatments will be randomly allocated to seven test sites of 2.2 cm diameter on the anterior surface of the forearms (from the antecubital fossa to the wrist).
	The skin blanching will be assessed by visual scoring.
Methodology:	The trial will consist of a screening phase, a test phase of 2 days, and, if applicable, a follow-up phase.
	Screening Phase (Day-15 to Day-1):
	Within 15 days before treatment a screening visit for trial eligibility of the subjects will take place:
	Medical history and concomitants therapies
	Physical examination, record of vital signs
	Urine pregnancy test for female subjects of child-bearing potential
	Check of inclusion/exclusion criteria
	Pre-test of blanching response
	Test Phase (Day 1 to Day 2):
	Subjects will receive investigational and reference products (matching vehicle and positive references) on Day 1.

Clinical Trial Protocol MC2-01-C4

Final Approved Version 20/08/2018

#### At Day 1:

Will be performed:

- Re-check of inclusion/exclusion criteria
- Urine pregnancy test for female subjects of child-bearing potential
- Selection of seven tests sites
- Application of the products under non-occluded conditions for 16 hours.

	
 
At Day 2:
 
Removal of the products
 
Visual assessments of the skin blanching by 2 trained observers 2 hours after the removal.
 
Assessment of the local tolerability.
 

	During the treatment phase local and systemic adverse events will be reported on an ongoing basis.
	Follow-up:
	If an adverse event (serious or non-serious), classified as reasonable_possible related to the trial medication is ongoing at the subject's last visit, a follow-up visit/contact will take place 14 (±2) days after that visit.
Total number of subjects (Planned):	60 subjects will be screened in order to have 36 subjects randomized and at least 30 subjects completed.
Number of clinical trial centers (Planned):	Single center
Region / country involved (Planned):	France
Clinical trial duration:	2 months
Duration of subject participation:	

Two days (plus the screening period and the follow-up phase).

CONFIDENTIAL

Inclusion criteria:	
 
Male or female subjects, aged 18 years to 50 years old, having signed and dated an informed consent,
 

	2. Non-smoker subjects,
	
 
Subjects demonstrating adequate vasoconstriction to Betamethasone Dipropionate (Augmented) cream within 15 day prior to dosing (unoccluded application of Betamethason Dipropionate (Augmented) cream for 4-6 hours must show a visua score of skin blanching of at least one unit (visual scale (0-4)),
 

	
 
Subjects without any signs of skin irritation/disease/disorders/symptoms or blemishes on test sites (e.g erythema, dryness, roughness, scaling, scars, moles, sunburn),
 

	
 
Female subject of non-child bearing potential, defined as surgicall sterile or post-menopausal (at least one year post cessation o menses),
 

	6. Female of childbearing potential who has been, in the opinion of the Investigator, using an approved method of birth control (e.g. ora contraception pill or patch, intra-uterine devices, contraceptive implants or vaginal rings, condoms, bilateral tubal ligation) at tria entry and agree to continue until the end of last trial visit.
	7. Female subjects of childbearing potential must have a negative uring pregnancy test at screening visit and at Day 1 to continue,
	8. Subjects willing and able to follow all the trial procedures and complete the whole trial,
	9. Subjects affiliated to a social security system
Exclusion criteria:	1. Female subjects who are breastfeeding,
	2. Use of topical corticosteroids on the test areas (forearms) within weeks prior to the screening phase,
	3. Use of systemic drugs which may interfere with the blanching reaction including, but not limited to, corticosteroids and other vasoactive drugs (nitrates derivatives, antihypertensive, phenylpropanolamine diphenhydramine, pseudo-ephedrine, antihistamines, non-steroida anti-inflammatory drug and aspirin/acetylsalicylic acid), within two weeks prior to screening visit,
	
 
Use of any other medication would interfere with the trial results, in particular topical drugs applied on the test area within two weeks prio to screening visit,
 

5. Subject's caffeine (i.e. coffee, cola, soft-drinks containing caffeine) intake greater than 500mg per day (1 cup of coffee contains

Page 6/54

#### Final Approved Version 20/08/2018

approximately 85mg of caffeine) within one day prior to screening visit and until the end of the last visit of the test phase,

- 6. Subject with a history of drug or alcohol abuse/addiction.
- 7. Subject with a history of calcium metabolism disorders,
- 8. Abnormal pigmentation of the skin or skin type, that could, in any way, confound interpretation of the trail results (skin type V to VI on the Fitzpatrick scale),
- 9. Subjects with obvious difference in skin color between arms,
- 10. Subjects with any of the following conditions present on the test areas: viral (e.g. herpes or varicella) lesions of the skin, fungal and bacterial skin infections, parasitic infections, atrophic skin, and *striae atrophicae*, fragility of skin veins, ichthyosis and ulcers,
- 11. Any current systemic or cutaneous disease that could in any way confound interpretation of the trial results (e.g. atopic dermatitis, contact eczema, or psoriasis),
- 12. Known or suspected hypersensitivity to any component(s) of IMP,
- 13. Subjects with current participation in any other interventional clinical, based on interview of the subject,
- 14. Subjects who have received treatment with any non-marketed drug substance (i.e. an agent which has not yet been made available for clinical use following registration) within the last 4 weeks prior to screening phase,
- 15. Previously enrolled in this clinical trial,
- 16. Subject who do not accept to avoid strenuous physical activity nor alcohol intake during the study.
- 17. In the opinion of the (sub)investigator, subjects who are unlikely to comply with the Clinical Trial Protocol (e.g. alcoholism, drug dependency or psychotic state),
- 18. Subjects in close affiliation with the trial personnel (e.g. immediate family member or subordinate), subjects being a member of the clinical trial personnel, or being an employee of the sponsor or a CRO involved in the trial,
- 19. Subjects impossible to contact in case of emergency,
- 20. Subjects who are in an exclusion period in the National Biomedical Research Register of the French Ministry of Health at randomization,
- 21. Subject under guardianship or hospitalized in a public or private institution, for a reason other than the research or subject deprived of freedom or under the protection of justice.

Page 7/54

# CONFIDENTIAL

Final Approved Version 20/08/2018

Investigational Product 1:	
Name / Internal code:	MC2-01
Pharmaceutical form:	Cream
Strength/Concentration:	Calcipotriol 0.005 % w/w (50 μg/g) and betamethasone dipropionate 0.064 %
	w/w (0.5 mg/g as betamethasone)
Route of administration:	Topical
	Twenty (20) μL / 2.2-cm diameter site
Dosage:	Twenty (20) µc / 2.2-cill diameter site
Investigational Product 2:	
Name / Internal code:	MC2-01 Vehicle
Pharmaceutical form:	Cream
Strength/Concentration:	NA
Route of administration:	Topical
Dosage:	Twenty (20) μL / 2.2-cm diameter site
Reference Product 1:	
Name / Internal code:	Clobex®
Pharmaceutical form:	lotion
Strength/Concentration:	Clobetasol propionate 0.05%
Route of administration:	Topical.
Dosage:	Twenty (20) μL / 2.2-cm diameter site
Reference Product 2:	
Name:	Betamethasone Dipropionate (Augmented)
Pharmaceutical form:	Cream
Strength/Concentration:	Betamethasone dipropionate 0.064% (equivalent to 0.05% betamethasone)
Route of administration:	Route of administration and dosage: Topical.
Dosage:	Twenty (20) μL / 2.2-cm diameter site
Reference Product 3:	
Name:	Locoid®
Pharmaceutical form:	Cream
Strength/Concentration:	Hydrocortisone butyrate 0.1%
Route of administration:	Topical.
Dosage:	Twenty (20) μL / 2.2-cm diameter site
Reference Product 4:	
Name:	Triamcinolone Acetonide
Pharmaceutical form:	Cream
Strength/Concentration:	Triamcinolone acetonide 0.1%
Route of administration:	Topical
Dosage:	Twenty (20) μL / 2.2-cm diameter site
Reference Product 5:	
Name:	Desowen®
Pharmaceutical form:	Cream
Strength/Concentration:	Desonide 0.05%
Route of administration:	Topical
Dosage:	Twenty (20) μL / 2.2-cm diameter site

CONFIDENTIAL

Final Approved Version 20/08/2018

Evaluation criteria:	The following evaluations will be performed during the trial:
	
 
Visual assessment of skin blanching:
 

	The visual assessment will be performed by two trained readers on Day 2 (2 hours after removal of products).
	Local tolerance / Systemic safety:
	- Local tolerability will be assessed by the Investigator at Day 2.
	- Daily record of AE.
Principal statistical methods:	MC2-01 cream will be compared with Clobex lotion, Betamethasone Dipropionate (Augmented) cream, Locoid ® cream, Triamcinolone Acetonide cream, Desowen cream and MC2-01 cream vehicle in terms of visual score of skin blanching 2 hours after a 16-hour application, using an ANOVA having subjects and treatments as factors. Estimates of treatment effect and 95% confidence interval of differences between MC2-01 cream and the reference products will be calculated from the model without correction for multiplicity in the primary analysis. Correction for multiplicity using Dunnett's test will be used as secondary analysis.
Subject Number Calculation:	In total 36 subjects will be randomized in the trial in order to have 30 completed evaluable subjects. Each subject will receive the MC2-01 cream, the 5 steroid-containing treatments and the MC2-01 cream vehicle on 7 different test sites. For details of calculation see section 12.5.
Trial dates:	First Subject In: Late August - Early September 2018 Last Subject Out: October 2018

CONFIDENTIAL

Clinical Trial Protocol MC2-01-C4

Final Approved Version 20/08/2018

Table 1 - Schedule of Assessments

Trial Phases: Screening		Test		Follow-up 	
Trial Days :	Day-15 to Day-1	Day1	Day2	Day15 (±2days)	
Informed Consent Form	Ŋ				
Demographics/Medical history	Ŋ				
Previous treatments/procedures	Ŋ				
Inclusion/exclusion criteria	$\checkmark$	$\checkmark$			
Selection of test sites		V			
Physical exam, vital signs	V				
Urine pregnancy test 	V	V			
Screening test for blanching response	V				
Randomization		$\checkmark$			
Local tolerance 			V	V	
Application of IMPs		V			
Product excess removal 			V		
Measurement of skin blanching by 2 trained evaluators 			Ŋ		
Concomitant treatments	V	V	V	V	
Adverse events	$\mathbf{V}$	V	$\mathbf{\overline{A}}$	V	
End of treatment			V		
End of study				V	

1: For female subject of childbearing potential. Result must be negative to continue the trial.

2: For subjects with a local tolerability scores >0 at Day 2 or if a non-serious adverse event classified as reasonably possibly related to the investigational products or an SAE is ongoing once a subject has completed the test phase (Day 2), a follow-up visit/contact (telephone contact or visit according to the investigator's discretion) will take place up to 14 ( $\pm$ 2) days after the end of test phase (D2). AEs and SAEs assessed reasonably possibly related to the trial medication must be follow until it is resolved or until the medical condition of the subject is stable.

3: 16 hours +/- 30 min after IMP application

4: 2 hours +/- 30 min after IMP removal

CONFIDENTIAL

Clinical Trial Protocol MC2-01-C4

Final Approved Version 20/08/2018

# **4** LIST OF ABBREVIATIONS AND DEFINITIONS OF TERMS

ADR	Adverse Drug Reaction
AE	Adverse Event
BDP	Betamethasone Dipropionate
CAL	Calcipotriol
CPCAD	Centre de Pharmacologie Clinique Appliquée à la Dermatologie = name of
	the trial site [ for Clinical Pharmacologie Center Applied to Dermatology]
CRF	Case Report Form
CRO	Contract Research Organization
CSR	Clinical Safety Responsible
DDS	Drug Delivery Solutions Aps
EU	European Union
FDA	Food and Drug Administration
FSI	First Subject In
GCP	Good Clinical Practice
ICH	International Conference on Harmonization
IEC	Independent Ethics Committee
IMP	Investigational Medicinal Product
IRB	Institutional Review Board
LSO	Last Subject Out
RDC	Remote Data Capture
SAE	Serious Adverse Event
SD	Standard Deviation
SOP	Standard Operating Procedure

Clinical Trial Protocol MC2-01-C4

# 5 BACKGROUND AND RATIONALE

## 5.1 Background

Psoriasis is a common, immune-mediated, inflammatory skin disease that is found world-wide. There is no cure for psoriasis. The goal of treatment is to reduce or eliminate its signs and symptoms. Mild to moderate disease is often treated with topical therapies. Among topical therapies, a combination treatment of a Vitamin D analog and a topical glucocorticosteroid has become especially popular. Several studies show that the combination of calcipotriol (CAL) and betamethasone dipropionate (BDP) is superior to each of the single agent (3) (4) (5). There is strong scientific rationale for the combination of vitamin D and glucocorticosteroids both with respect to efficacy and safety (6) (7) (8), and combination treatment with a Vitamin D analog and a topical corticosteroid is recommended in both American and European guidelines (9) (10) (11) (12).

Calcipotriol and betamethasone are incompatible in an environment, since CAL requires basic conditions to maintain stability while betamethasone requires acidic conditions. Currently marketed products are therefore restricted to non-, oil-based formulations.

Sponsor has developed the MC2-01 cream containing the fixed dose combination 0.005 w/w% CAL (as anhydrate) and 0.064 w/w% BDP using the proprietary PADTM Technology which protects the drug substances from degradation during storage. The MC2-01 cream is easy to apply, and the cosmetic appearance is that of a white, easily-spreadable cream that absorbs completely into the skin a few minutes after application and it is expected that MC2-01 cream will differentiate from marketed formulations of CAL/BDP by patient preference for the cream.

The investigational products (IMP) in the present trial are:

- MC2-01 cream (0.005% w/w CAL, 0.064% w/w BDP),
- MC2-01 cream vehicle.

The dosage of the active agents of the presently tested formulation are 0.005% w/w for calcipotriol and 0.064% w/w for betamethasone (as dipropionate). These concentrations are similar to the ones of the commercially available formulations of calcipotriol and betamethasone dipropionate or the combination of both.

## 5.2 Rationale for the trial

## 5.2.1 Rational for the trial design

The human skin blanching assay (vasoconstriction test) described by R. Stoughton and A.W. McKenzie in 1962 (1) has been used for many years by pharmaceutical companies and was accepted by the FDA as a mean to assess the clinical potency of topical corticosteroid formulations. The assay is typically performed with healthy volunteers and with intraindividual comparisons and is based on the ability of corticosteroids to produce skin blanching i.e., vasoconstriction in the dermal microvasculature. The

Clinical Trial Protocol MC2-01-C4

degree of skin blanching is a measure of inherent potency of the drug and its capacity to diffuse through the stratum corneum.

The original human skin blanching assay (1) used a 16-hour application and visual assessments of the degree of vasoconstriction. Since then, numerous attempts to refine this assay have been done, e.g., by changing the application time and by including colorimetric assessments of the skin color.

The most comprehensive comparison of the vasoconstrictor assay with clinical potency was in the trial by Cornell and Stoughton (2) of over twenty glucocorticoid formulations which involved the comparison of 2 formulations in both the vasoconstrictor assay and double-blind clinical studies in psoriasis. Thirty subjects in each vasoconstrictor and 30 or more subjects in each clinical trial/group (psoriasis) paired comparison was used. In all but two, the comparisons directly agreed with the clinical potency as determined by the bilateral, paired, double-blind studies in psoriasis. All these correlations were done with the single reading (at least 2h after the product removal procedure) after 16h of exposure under a guard (13).

Ranking of the clinical potencies of USA glucocorticoid topical formulations has been based on the Stoughton's skin blanching assay.

# 5.2.2 Rational for the reference products

In the US potency ranking of commonly used corticosteroids, Group I is the super-potent category. Potency descends with each group to group VII, which is the least potent.

In a ranking assay, the active reference products must be selected to ensure an adequate bracketing to determine the topical corticosteroid potency class of the MC2-01 cream (CA/BDP). It should also demonstrate that the IMP is not different from the target class representative.

The active reference products are listed below including their steroid potency description and Group and Class according to the 7-point US classification system. Several US classification charts (13) (14) (15) (16) and the WHO classification (17) have been used for reference and selection.

Generic name	Group /Class	Potency	Brand name	Rational
Clobetasol propionate 0.05%	I	Ultra High/Super potent	Clobex ® lotion	Highest potent
Betamethasone dipropionate 0.05 %	II	High/Potent	Betamethasone Dipropionate (Augmented) cream	Representative of the target potency group and matching steroid for the IMP
Triamcinolone acetonide 0.1%	IV	Medium	Triamcinolone Acetonide cream	Representative of a medium group
Hydrocortisone-17- butyrate 0.1%	V	Medium	Locoid ® cream	Representative of a lower medium group
Desonide 0.05%	VI	Low	Desowen ® cream	Lowest potency used in psoriasis (face or folds)

Page 17/54

This document will be regarded as confidential and proprietary in nature and will not be disclosed to any third party without sponsors written consent

Clinical Trial Protocol MC2-01-C4

Final Approved Version 20/08/2018

Group: From Stoughton (13), the American Academy of Family Physicians (16) and World Health Organization Classification of Topical Corticosteroids (17).

Class: Potency of Topical Corticosteroids (USA classification) (14).

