#### 13.2.1 Primary pharmacodynamic criterion

The analysed variable will be the mean between the two readers at each evaluation time.

The results will be expressed by the mean values obtained at each assessment time by product/site.

MC2-01 cream will be compared with Clobex lotion, Betamethasone Dipropionate (Augmented) cream, Triamcinolone Acetonide cream, Locoid® cream, DesOwen cream and MC2-01 cream vehicle in terms of visual score of skin blanching 2 hours after a 16 hours application, using an ANOVA with subjects and treatments as factors. The mean of visual assessments obtained at the same time points from 2 independent trained readers will be used. In case of a significant treatment effect, estimates of treatment effect and 95% confidence interval of differences between reference products and MC2-01 cream will be calculated from the model without correction for multiplicity in the primary analysis. Correction for multiplicity using Dunnett's test will be used as secondary analysis. In case of significant deviation to the normal assumption, a non-parametric approach with Kruskall-Wallis test for the overall product effect and Wilcoxon's Sign Rank Test for the pairwise comparisons will be used.

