#### **13.4** General principles

All significance tests will be two-sided and all confidence intervals will be presented with 95% degree of confidence.

Categorical data will be summarized using the number and percentage of subjects in each category. Continuous data will be summarized using the mean, median, SD, minimum and maximum values.

Very few missing values from primary response criterion are expected. Usually less than 10% of randomized subjects do not attend the last visit in this kind of studies. Drop-outs and missing values will be accounted for by the analysis of end of treatment values using a last observation carried forward approach and by the definition of the trial analysis sets prior to unblinding. All the pre-specified analyses will be reviewed in relation to the blinded data actually obtained and the Statistical Analysis Plan Update will be finalized before breaking the randomization code.

Clinical Trial Protocol MC2-01-C4

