### 13.5 Number of subjects calculation

The null hypothesis for each pairwise comparison will be no difference in the human skin blanching test :

H0: ∆ = 0,

where  $\Delta$  is the mean difference in visual score between test sites with the compared treatments. The standard assumptions of normality and independence will be used.

According to previous vasoconstriction trial performed by CPCAD, a maximal standard deviation for the difference of 0.65 is assumed.

Using a paired t-test, a two-sided significance level of 5%, with 30 complete subjects, the probability of detecting a difference of 0.5 units assuming a standard deviation for the difference of 0.65 is 98%.

MC2-01 cream will be compared to the five steroid-containing reference products giving at least 92% (0.98) power to obtain 5 significant differences if the true difference with each reference product is at least 0.5 int. MC2-01 cream will also be compared to the matching MC2-01 cream vehicle, but that will have negligible impact on the overall power assuming a difference of at least 1 point between both products.

A total of 36 subjects will be randomized in this trial in order to obtain at least 30 completed evaluable subjects.

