## 5.2 . Analysis of pharmacodynamic effect (blanching)

#### 5.2.1 Primary pharmacodynamic criterion

The analysed variable will be the mean between the two readers at each evaluation time.

The results will be expressed by the mean values obtained at each assessment time by product/site.

MC2-01 cream will be compared with Clobex® lotion, Betamethasone Dipropionate (Augmented) cream, Triamcinolone Acetonide cream, Locoid® cream, DesOwen® cream and MC2-01 cream vehicle in terms of visual score of skin blanching 2 hours after a 16 hours application, using an ANOVA with subjects and treatments as factors.

Some minor changes in the protocol statistical methods have been decided and reported in the SAP to improve the data analysis of the primary criterion.

The protocol planned that In case of a significant treatment effect, estimates of treatment effect and 95% confidence interval of differences between reference products and MC2-01 cream will be calculated from the model without correction for multiplicity in the primary analysis and that correction for multiplicity using Dunnett's test will be used as secondary analysis. In case of significant deviation to the normal assumption, a non-parametric approach with Kruskall-Wallis test for the overall product effect and Wilcoxon's Sign Rank Test for the pairwise comparisons will be used

The present Statistical Analysis Plan states that In case of a significant treatment effect, the comparisons between reference products and MC2-01 cream will be done from the model with correction for multiplicity using Dunnett's test directly in the primary analysis. For each fitted model, residual plots will be used to check the model assumptions. If there is an obvious deviation to these assumptions, the analysis will be done on the rank-transformed data.

The data will be also presented graphically by treatment using boxplot of visual assessment of skin blanching.

Statistical Analysis Plan MC2-01-C4 / CPCAD CPC-3530 Version 2.0 dated 05-Dec-2018 Page 14/16

The results will be presented as follows:

	MC2-01 cream (n=XX)	Clobex® lotion (n=XX)	Betamethasone Dipropionate (Augmented) cream (n=XX)	Triamcinolone Acetonide cream (n=XX)	Locoid® cream (n=XX)	Desowen® cream (n=XX)	MC2-01 cream vehicle (n=XX)
N Mean±SD Median (Min,Max)							
p-value a (treatment comparison versus MC2-01 cream)	-						

a: method used for multiple comparisons

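### A non-significant test with no margin cannot show that MC2-01 is not different from the Class II cream, and the SAP results table gives no interval for the difference

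*Protocol*

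**What the plan says.** **Aim for this pair.** Protocol 5.2.2 (reference products) says of the ranking assay: "It should also demonstrate that the IMP is not different from the target class representative". The table there names betamethasone dipropionate (augmented) cream, Class II, as that representative. The clinical hypothesis in the synopsis expects MC2-01 to blanch less than Clobex and to be "not significantly different from Betamethasone Dipropionate (Augmented) cream and higher than the other references".

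**Formal objective.** Protocol 6.1 and SAP 2.1 say only that the products are to be compared. Neither document writes a success rule.

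**Hypothesis.** Protocol 13.5: "The null hypothesis for each pairwise comparison will be no difference in the human skin blanching test", that is, a mean difference of zero. Neither document gives an equivalence or non-inferiority margin. The same section states that "a maximal standard deviation for the difference of 0.65 is assumed".

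**Planned output in the protocol.** The synopsis says that "95% confidence interval of differences between MC2-01 cream and the reference products will be calculated from the model without correction for multiplicity". Section 13.2.1 likewise says that, after a significant overall treatment effect, "estimates of treatment effect and 95% confidence interval of differences between reference products and MC2-01 cream will be calculated from the model". Dunnett's test is secondary there.

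**Planned output in the SAP.** Section 5.2.1 recites the protocol plan and then says the comparisons will be "done from the model with correction for multiplicity using Dunnett's test directly in the primary analysis". Its results table lists, for each product, N, mean and SD, median and range. The only comparative row is a p-value against MC2-01. If residual plots show an obvious departure from the assumptions, the analysis moves to ranks. Section 5.4.1 excludes any subject with a missing primary score.

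**The concern.** Section 5.2.2 uses the verb demonstrate, and the synopsis turns this into absence of significance. A difference test cannot do that work. A large p-value arises when two products are alike, and also when they differ by an amount the trial was not precise enough to resolve. Without a margin, nothing says how close is close enough.

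This is the pair that places MC2-01 in its target potency class. The protocol's interval would at least have shown which differences remained compatible with the data. The SAP table leaves the reader with a p-value, and the stricter Dunnett threshold makes non-significance easier to reach for exactly this pair.

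**Working it through.** **Inputs.** From Protocol 13.5: SD of the within-subject difference 0.65, 30 completers, two-sided 5%, difference to detect 0.5. From Protocol 13.2.1 and SAP 5.2.1: ANOVA with subject and treatment as factors, 7 products, 6 comparisons with MC2-01.

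**1. The plan's own figure.** Paired t-test, df = 29, noncentrality = 0.5 / (0.65/√30) = 0.5 / 0.1187 = 4.21. Power is 98.3%, against 98% stated. For five comparisons treated as independent, 0.983^5 is about 92%, as stated. The sample size reproduces, but it is power to find a difference, and its five steroid comparisons include the Class II cream.

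**2. Smallest observed difference that is significant.** Standard error 0.65/√30 = 0.1187; residual df = (30 − 1) × 6 = 174.
- Unadjusted: t(0.975, 174) = 1.974; 1.974 × 0.1187 = 0.234 units.
- Dunnett, 6 comparisons, correlation 0.5: critical value 2.592; 2.592 × 0.1187 = 0.308 units.

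**3. Chance of a non-significant result when the products truly differ.** For a true gap d, this is the probability that a noncentral t (df 174, noncentrality d/0.1187) lies within ± the critical value.

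| True gap | Unadjusted | Dunnett |
|---|---|---|
| 0.2 | 61% | 81% |
| 0.3 | 29% | 52% |
| 0.4 | 8% | 22% |
| 0.5 | 1% | 5% |

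**4. Sensitivity.** Protocol 13.4 says: "Usually less than 10% of randomized subjects do not attend the last visit in this kind of studies". I take 33 of 36 completing as an assumption (df = 32 × 6 = 192; critical values 1.972 and 2.590).
- SD 0.65: 25% vs 47% at a gap of 0.3; 6% vs 17% at 0.4.
- SD 0.5 (assumed, because the protocol calls 0.65 maximal): 37% vs 61% at 0.2; 7% vs 20% at 0.3.

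A smaller SD moves the problem to smaller gaps but does not remove it.

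**5. What a margin would need.** The documents give none, so these are illustrations: chance that the whole CI lies within ± the margin, 30 completers, SD 0.65, true difference 0. Ranges run from df 29 to df 174.

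| Margin | 90% CI | 95% CI |
|---|---|---|
| 0.5 | 99% | 97% |
| 0.4 | 90–91% | 81–84% |
| 0.3 | 59–62% | 38–42% |

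A true gap of 0.3 would pass a 0.5 margin 50–51% of the time with a 90% CI and 37–39% with a 95% CI. The 0.5 in Protocol 13.5 is a difference to detect. It is not one declared unimportant, so it cannot be borrowed as a margin.

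**The case against.** **The objective is only to compare, and this is a ranking trial.** True. No decision is formally tied to non-significance, and 5.2.2 is a rationale for choosing comparators. A reader might infer that the primary analysis is invalid or that the trial has a faulty success rule; the documents support neither. The fault lies in how the synopsis and 5.2.2 say this pair is to be read.

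**The protocol's CIs still stand.** Also fair: the SAP does not expressly withdraw them, and a missing table row does not prove they will go unreported. But the SAP describes them as what the protocol planned, then states its own approach without them. A reader of the SAP cannot tell.

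**The interval can be recovered.** On the untransformed, complete-case path, largely yes. All six comparisons share one standard error and known df, so a mean difference of 0.30 with a Dunnett p of 0.059 gives t = 2.53, SE = 0.30/2.53 = 0.119 and a 95% CI of 0.07 to 0.53. On that path the gap is one of display. Under the rank fallback the recovery fails, because the p-value no longer refers to score units.

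**Two stronger readings should be resisted.** A reader might set that Dunnett p of 0.059 against the unadjusted CI of 0.07 to 0.53 and call it a contradiction. It is not: one is adjusted and the other is not. The matching Dunnett interval, 0.30 ± 0.31 or −0.01 to 0.61, includes zero. A reader might also infer that Dunnett makes the whole hypothesised ranking harder to obtain when MC2-01 and the Class II cream are alike. That depends on the SD. With bracketing gaps of 0.5, a vehicle gap of 1.0 and 33 completers, the chance of the full pattern (unadjusted vs Dunnett) is 93% vs 88% at SD 0.65 but 95% vs 99% at SD 0.5.

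**A CI without a margin does not prove similarity either.** Correct. It shows what remains compatible with the data; it does not settle a formal claim.

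**Conclusion.** The point holds in a limited form and should be fixed. As worded, 5.2.2 and the synopsis treat non-significance as a demonstration of no difference, and a zero-difference test without a margin cannot support that. At SD 0.65 with 30 completers, the threshold for significance is about 0.31 units under Dunnett and 0.23 unadjusted. A true gap of 0.3 then goes undetected in 52% and 29% of trials respectively. These figures assume normal differences, equal variances across comparisons, and the protocol's SD, which it calls maximal; a smaller SD lowers them at any given gap.

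The missing interval is a SAP reporting omission. It is recoverable by back-calculation on the main path and not under the rank fallback. Dunnett as the primary test is not itself the error, and the sample size need not change for the reporting fix.

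**What to change.** In SAP 5.2.1, before the code is broken:

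1. Add to the results table the estimated difference and its 95% CI for all six comparisons, each CI labelled unadjusted or Dunnett-simultaneous. If the rank fallback is used, still report an interval in score units for MC2-01 minus betamethasone dipropionate (augmented), from the untransformed model or as a Hodges-Lehmann interval on the within-subject differences.
2. State that non-significance for this pair means no difference was detected, that it does not by itself demonstrate similarity or Class II, and that the CI is given to show which differences remain compatible with the data.
3. Choose one course for the claim itself. If it is kept as a formal claim, pre-specify a justified margin and the CI level. If not, reword Protocol 5.2.2 and the synopsis hypothesis as descriptive.

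Dunnett can stay primary. Items 1 and 2 cost two table rows and a short statement, with no extra subjects. A formal margin costs more: at SD 0.65 and no true difference, 30 completers give about 90% power with a 90% CI at a margin of 0.4, but only about 60% at 0.3. The downside is that similarity may have to be reported as inconclusive.
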